Based on patient scheduling, there are approximately 4-6 new patients every week who would be a potential Patient. We will need to recruit 50% of those potential Patients over a 6-month course.

It will only be those doctors (residents) and research assistants listed on the study involved in recruiting patients. Once COVID is over, we will have research assistant involvement outside of residents and will make an addendum to the application to include them in the future.

Our facilities will offer tablets which Participants can use to answer surveys. The tablets are approved by HUMC Hospital Admin for use in clinic. The tablets belong

Patient reported outcomes from patients seen in virtual phone visits compared to in-person physical visits for post-operative follow-up at a sports medicine clinic: a prospective randomized controlled trial

to HUMC and the IT department will help us set them up. The tablets will be secured in the physician work area under lock and key.

The facilities staff will be notified that this study is taking place, so that if a Participant contacts the staff about the study, they know who to redirect and call.

The surveys are to be completed by all participants of the study. Surveys are on REDCaps hosted by Lundquist (<https://research.lundquist.org/redcap/surveys/?s=NK3YH4NWL3>) and are done online. This study will deliver the surveys in the same manner to participants that attend in-person visits and virtual visits. REDCaps will allow us to collect participants' clinical data. The REDCap administrator is aware that these surveys are collected for research purposes. The surveys will result in a score. This score from REDCaps will be part of the DHS medical record. Any Participant that is part of the study and present for an in-person post-operative appointment will receive a tablet to complete the survey after their appointment. Any Participant in the virtual phone group will receive an email with the survey to complete after attending a virtual phone visit or if the Participant is having difficulty, one of the research staff go through the questions with the Participant over the phone.

8) Prior Approvals

No prior approvals are needed for this study.

9) Study Design

a) Recruitment Methods

When: Participants will be recruited at the pre-op visit, day of surgery, or in-person 2-week post-operative visit.

Where: The Participant will be recruited at Harbor-UCLA Medical Center in-person.

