The Participant will be notified at the 2-week post-op or after if they will receive in-person follow up or virtual phone follow-up. If the Participant in the virtual phone group feel they need an in-person visit, the Participant will be free to make an in-person follow-up. After each follow up visit (6-week, 12-week, and 6-month), the Participant will be asked to fill out 30-minute surveys.

The surveys the Participant will be asked to fill out are the following:

1. KOOS- a knee specific survey
2. Quick Dash Outcome Measure
3. PROMIS Global
4. General Health Questionnaires (2)
5. Patient Satisfaction Survey -We will have the patient complete this also after every visit to see if their preferences change over time as their recovery changes.

If a Participant attends an in-person post-operative follow up visit, then the study team member will check to see if the participant is on the in-person list. If the participant is on the list, then he or she will be given a tablet to fill out the online survey after the appointment. The tablet will be set up so a link to the surveys can be accessed and participants can fill out the surveys. The surveys are on REDCaps (<https://research.lundquist.org/redcap/surveys/?s=NK3YH4NWL3>). Patients will be able to fill out the survey at home. For Participants that attend a virtual appointment, an online

Patient reported outcomes from patients seen in virtual phone visits compared to in-person physical visits for post-operative follow-up at a sports medicine clinic: a prospective randomized controlled trial

link to the survey on REDCap will be sent to the Participant's email. Members of the study team can also call the participant to conduct the survey over the phone. The emails will be made secure by having them sent out from an official DHS email that uses Microsoft outlook and requires double verification to logon. The content of the email message is included in the IRB submission as a separate document.

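### The protocol says both groups receive the surveys in the same way, but default route, setting and timing differ by arm, and no common completion window or phone-help rule is described

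*Combined protocol and SAP*

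**What the plan says.** Section 7 (Resources) places the surveys online in REDCap for everyone and states: "This study will deliver the surveys in the same manner to participants that attend in-person visits and virtual visits". The same paragraph then gives two routes. Study participants "present for an in-person post-operative appointment will receive a tablet to complete the survey after their appointment". For the other arm the default is a link: "Any Participant in the virtual phone group will receive an email with the survey to complete after attending a virtual phone visit". The paragraph also provides a fallback for that arm, with help from study staff: "if the Participant is having difficulty, one of the research staff go through the questions with the Participant over the phone".

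Section 9g (Procedures) repeats the split. For someone attending in person, staff check the in-person list: "If the participant is on the list, then he or she will be given a tablet". Still in the text on in-person attendance, it adds: "Patients will be able to fill out the survey at home". After describing the emailed link for virtual appointments it says: "Members of the study team can also call the participant to conduct the survey over the phone". Both arms share one anchor: surveys follow each 6-week, 12-week and 6-month visit.

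Section 10 (Risks) lets participants choose a convenient time after a virtual visit. It has in-person participants answer after theirs, and lists a 30-minute longer stay for the tablet survey as an inconvenience. It also allows incompletely answered surveys to be removed.

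Section 9f makes PROMIS Global primary, and KOOS, QuickDASH and appointment satisfaction secondary. Section 9i compares scores at each time point by Student t-test, visit preference by chi-squared test, and satisfaction over time within each group by analysis of variance. It does not mention how or when a survey was completed.

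**The concern.** Randomisation balances the patients but not the way their answers are collected when collection depends on the arm. If the plan is followed as written, one arm will tend to answer in the clinic just after the visit, and the other at home, at a later time of their choosing, sometimes with a member of the study staff asking the questions. The planned tests would attribute any resulting difference in scores to the type of visit. A true difference could be hidden in the same way.

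The endpoints are not equally exposed. Satisfaction is the most exposed, because some participants would rate the visit while still in the building and others might give their rating to study staff. For PROMIS Global the plausible route is timing: patients are recovering, and with no described window an emailed survey may be answered later in recovery than a same-day tablet survey. Because incomplete surveys may be dropped, unequal completion by route could also change who is analysed.

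**Working it through.** **1. The descriptions side by side**

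| Feature | In-person | Virtual | Common? |
|---|---|---|---|
| Instrument, platform | REDCap, online | REDCap, online | Yes |
| Anchor | After each visit | After each visit | Yes |
| Default route | Clinic tablet (7, 9g) | Emailed link (7, 9g) | No |
| Setting | Clinic (10); home allowed in the in-person text of 9g | Away from clinic | Partly |
| Timing | After the visit (10) | Time chosen by the participant (10) | No common window |
| Staff phone help | Not described for this arm | If in difficulty (7); no condition repeated (9g) | No |

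The common-delivery sentence therefore holds for the first two rows only. The home option makes the link between arm and mode partial.

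**2. The plan's sample size**

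Inputs from section 9i: alpha 0.05, power 80%, effect size 0.8. I assume a two-sided test, since sidedness is not stated. The two-sample t-test needs 25.52 per group, rounded up to 26, which matches the plan. Power at 26 per group is 0.807.

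**3. What an arm-linked shift would do**

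The documents give no mode effect, so the shift b (in SD units) is assumed: 0.1, 0.2 or 0.3. For n per arm the t statistic has 2n − 2 degrees of freedom and noncentrality b × √(n/2).

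- n = 26: √13 = 3.606, giving noncentrality 0.361, 0.721, 1.082; critical value 2.009 on 50 df.
- n = 52 (the recruitment target of at least 104 in section 9c, if all were analysed): √26 = 5.099, giving 0.510, 1.020, 1.530; critical value 1.983 on 102 df.

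For power I take the case where the shift opposes the plan's 0.8 SD, leaving 0.8 − b. A shift in the other direction would inflate the observed difference instead.

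| Assumed shift b | False positive, n = 26 | False positive, n = 52 | Power at 0.8 − b, n = 26 | Power at 0.8 − b, n = 52 |
|---|---|---|---|---|
| 0 | 5% | 5% | 81% | 98% |
| 0.1 | 6.4% | 8.0% | 70% | 94% |
| 0.2 | 10.9% | 17.3% | 56% | 86% |
| 0.3 | 18.6% | 32.9% | 42% | 71% |

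Each figure is for a single t-test. Recruiting to 104 protects power but makes the false-positive problem worse, because a fixed bias is easier to detect with more patients.

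**4. Dilution by home completion**

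If half the in-person arm also completed at home, the contrast in mode would halve, to 0.05, 0.10 or 0.15 SD. At 26 per arm the false-positive rate would then be 5.4%, 6.4% or 8.3%, and power 76%, 70% or 63%.

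**The case against.** The strongest reply is that the common-delivery sentence comes just after the statement that surveys are online in REDCap, so it may mean only one instrument on one platform. The two routes are then set out openly. This stands in part: the instrument is common and nothing is concealed. But the sentence speaks of delivery, and delivery differs.

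A reader might infer that sections 7 and 9g contradict each other on phone help and tablets. The documents do not show that. The phone sentence in 9g directly follows the text on virtual appointments and reads as section 7's option restated without its condition. On tablets, section 7 covers anyone attending in person, which includes a virtual-group participant who comes in; 9g is silent on that case rather than excluding it. Each rule should be stated once, but this is a matter of clarity.

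A reader might also infer that mode is not recorded at all. The surveys are attached to the protocol and were not available for this review, and "The content of the email message is included in the IRB submission as a separate document". Section 9g lists who completes the form and time since surgery among the data collected, which may capture part of it. What can be said is that the visible text describes no window and no use of mode in the analysis.

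Finally, the tablet secures an answer while the participant is present. Replacing it with email could trade an unknown mode effect for unknown non-response. That objection stands and shapes the recommendation.

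**Conclusion.** The concern holds in this limited form: the plan claims a uniformity of delivery that its own procedures lack, and the planned unadjusted comparisons cannot separate mode and timing of completion from visit type. It should be corrected, with medium confidence. It is strongest for satisfaction and weaker for PROMIS Global.

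It would go too far to say that mode is fully confounded with arm, since home completion is allowed, or that the primary result will be biased, since nothing in the documents gives the size or direction of a mode effect. The range of 6% to 19% at 26 per arm (8% to 33% at 52) rests wholly on assumed shifts of 0.1 to 0.3 SD applied to a whole arm, a two-sided test and complete data. With dilution it falls to about 5% to 8% at 26 per arm. The consequence could be negligible or material.

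**What to change.** Reconcile sections 7, 9g and 10 so that both arms have:

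- the same completion window after each 6-week, 12-week and 6-month visit;
- the same reminders;
- the same option to complete at home by REDCap link;
- the same condition for staff phone help.

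State once what a virtual-group participant who attends in person receives. Record mode (self at home, self in clinic, staff by phone) and completion date if the survey does not already do so. Report mode, days from visit to completion, and response by arm. Keep any comparison by mode descriptive, because mode is determined after randomisation. Reword the common-delivery sentence to say what is shared (instrument, platform, window, help rule) and what is not.

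Emailing the link to everyone instead of using the tablet would go further, but it is for the investigators to weigh, since in-person response may fall by an amount the documents do not allow one to estimate.

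The cost is low: protocol wording, perhaps one REDCap field, reminder and phone-help text in English and Spanish, and an IRB update that includes the filed email text. Internet access is already an inclusion criterion (9b) and email addresses are already on the study list (9j). The recording should be in place before data collection, because unrecorded mode may not be recoverable later.

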Researchers want to allow patients to have enough time to read the information sheet and consider participation in this study.

In-person consent will be done at any in-person visit including the pre-operative appointment, day of surgery, and at the routine 2-week postop visit.

How: The Participant will be recruited in-person.

Source of the Participants: Patients that present to the Harbor-UCLA Medical Center sports medicine clinic that have scheduled operative intervention.

Methods to identify potential Participants: When patients of the sports medicine clinic have planned operative intervention, study team member will go through the patient charts to see if patient meets criteria and then discuss and consent the Participant in-person.

Materials to recruit Participants: Patients who meet criteria will be given the information study sheet to review on their own.

Patient reported outcomes from patients seen in virtual phone visits compared to in-person physical visits for post-operative follow-up at a sports medicine clinic: a prospective randomized controlled trial

There are no payments to any of the Participants.

b) Inclusion and Exclusion Criteria

Inclusion criteria:

Participants are at least 18 years of age. Participants who are seen at Harbor-UCLA Medical Center sports medicine clinic. Participants have agreed to have operative intervention. Participants must own a phone with reliable calling capabilities. The Participants must have access to reliable internet to fill out the online survey. The Participants must be able to provide consent. Participants may include pregnant patients. Participants who start out in the virtual phone pathway, and the clinician deems person to require an in-person appointment at the 2-week follow-up visit can be moved to the in-person pathway.

Exclusion criteria:

Patients that are under the age of 18, any cognitive impaired adult, and any adult unable to provide consent.

c) Local Number of Participants

For a statistical significance of 0.05, Power of 80%, and assuming a medium effect size of 0.8, 26 patients are required per group for a total of 52 Participants.

The number of Participants need to complete the research procedure are 52.

Locally we will attempt to recruit at least 104 Participants. This will allow room in case of patients are removed or fall from the study.

d) Study-Wide Number of Participants

This is not a multicenter study.

e) Study Timelines

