The study will be ongoing until the appropriate number of Participants are recruited from this site.

The duration of an individual Participant's participation in the study will be from initial visit where consent is asked until completion and submission of the surveys at their 6-month post-operative appointment.

The duration anticipated to enroll all study Participants will be 6 months.

The estimated date for the investigators to complete this study (complete primary analyses) is December 2023.

f) Study Endpoints

Primary study endpoints: Participant reported outcome scores through PROMIS Global.

Patient reported outcomes from patients seen in virtual phone visits compared to in-person physical visits for post-operative follow-up at a sports medicine clinic: a prospective randomized controlled trial

Secondary study endpoints: Patient survey scores for knee injuries via KOOS, and shoulder and elbow injuries via QuickDash. Patient appointment satisfaction scores will be surveyed.

g) Procedures Involved in the Human Research

There are no procedures performed.

The mentioned above surveys will be attached to this document.

Study Design:

In this prospective study, we will enroll patients undergoing operative intervention at a Sports Medicine clinic.

The patient will arrive at the 2 week post-operative appointment to sign the consent form in the presence of study team member and a witness in order to be eligible to participate in the study.

After consent is obtained, the Participant will be randomized to either in-person follow up or virtual phone follow up to take place after the 2-week post-op visit. The virtual visits will occur using the same platforms that they are currently taking place in accordance and required by LA County DHS/HUMC.

The randomization process will utilize block randomization and be conducted by an online program called <http://www.randomization.com>. (Wichmann and Hill, 1982, as modified by McLeod, 1985). The Participant will be assigned a number based on the order the Participant is enrolled in the study and that number will be randomly assigned to a follow-up group based on that number.

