All participation and questionnaires in this study are optional. It is made clear to the Participants that their participation is voluntary. If Participants would like additional appointments, they are free to contact their provider to schedule another one.

Participants that are in the virtual phone group are free to contact their provider to schedule an in-person visit if they choose to or if their provider would like to see them for an in-person visit. Participating in the study, completing the surveys will not impact the quality of care provided to the participant.

13) Compensation for Research-Related Injury

This research does not involve more than minimal risk.

14) Economic Burden to Participants

There is no economic burden to Participants. There is the burden of time to participate and fill out the survey.

Patient reported outcomes from patients seen in virtual phone visits compared to in-person physical visits for post-operative follow-up at a sports medicine clinic: a prospective randomized controlled trial

15) Consent Process

The Participants will be identified as patients presenting at the Harbor-UCLA Orthopaedics Sports medicine clinic who agree to operative intervention. Patients will receive a study consent form to review on their own. The study team member will go through the patient charts to determine patients that meet the inclusion criteria and then provide the patient with the study consent form. At the pre-operative visit for surgical planning and signing of the surgical consents, all patients will be given a study consent form and asked to participate in the study. The study will be explained to the patient, questions will be encouraged and answered, and the patient will be asked to sign the consent if they wish to participate in the study.

A member of the research team will make it clear that the patient can come in for an in-person visit if they wish and at any time for their post-operative care. The patient can also choose to spend more time to considering participating in the study.

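### Consent timing is contradictory and randomisation is tied only to consent, so allocation can precede the 2-week assessment at which virtual-arm patients, and only they, can be moved

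*Combined protocol and SAP*

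**What the plan says.** **Consent.** Section 9g (Study Design) states: "The patient will arrive at the 2 week post-operative appointment to sign the consent form". The same sentence makes this a requirement for eligibility. Section 9a says "Participants will be recruited at the pre-op visit, day of surgery, or in-person 2-week post-operative visit" and, on consent itself, "In-person consent will be done at any in-person visit including the pre-operative appointment, day of surgery, and at the routine 2-week postop visit". Section 15 says "At the pre-operative visit for surgical planning and signing of the surgical consents, all patients will be given a study consent form" and has them asked to sign if they wish to take part. A later paragraph of section 15 has eligible patients approached either before surgery or at the 2-week visit, without listing the day of surgery.

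**Randomisation.** Section 9g: "After consent is obtained, the Participant will be randomized to either in-person follow up or virtual phone follow up". Numbers are given in order of enrolment. No visit, date or position relative to the clinical assessment is stated. The participant learns the allocation at the 2-week visit or later.

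**Moves.** Section 9b, under inclusion criteria, provides for "Participants who start out in the virtual phone pathway, and the clinician deems person to require an in-person appointment at the 2-week follow-up visit" and lets them change to the in-person pathway. No move in the other direction is described. Sections 9g, 12 and 15 also leave virtual-arm patients free to be seen in person later.

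**Analysis.** Section 9i compares the in-person and virtual phone groups by Student t-test at each visit. It does not say whether a moved patient is counted in the assigned group or in the pathway followed.

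**The concern.** Read literally, a patient who signs only before surgery complies with sections 9a and 15 and fails the eligibility condition in 9g. That needs correcting in its own right, but the statistical issue is the order of allocation and assessment.

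A patient can be moved out of the virtual pathway at 2 weeks only if already assigned to it. The rule in 9b therefore presupposes allocation before the clinician's decision. The decision is a clinical judgement, so it is probably related to how recovery is going, and it changes the pathway in one arm only. In-person patients with the same recovery stay where they are.

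What follows depends on a choice the plan does not make. If moved patients are counted by pathway, the virtual group loses a selected subset and the comparator gains it, so the groups are no longer those formed by randomisation. If moved patients are counted as randomised, comparability is kept but part of the virtual arm receives the comparator, which shrinks the contrast.

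**Working it through.** **1. Order of events.** Two sequences are both compatible with the text:

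- Consent before or on the day of surgery (9a, 15), randomisation at some point after consent (9g), 2-week assessment, possible move (9b).
- Consent on arrival at the 2-week visit (9g), randomisation, clinician's assessment at the same visit, possible move (9b).

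In both, allocation precedes the assessment. The second shows that settling the consent wording would not, by itself, prevent the move. The phrase in 9g about what happens after the 2-week visit follows the words for the two kinds of follow-up and more naturally dates the follow-up than the act of randomising. The later notification in 9g concerns what the participant is told. It does not date the allocation or say that the clinician is unaware of it.

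**2. The plan's own figure.** Inputs from 9c and 9i: alpha 0.05, power 80%, standardised effect 0.8. Sidedness is not stated. A two-sided t-test needs 25.5, so 26 per arm, with power 0.807. The stated 26 per group reproduces. The one-sided normal approximation gives 20 and does not.

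**3. Counted by pathway.** Assume equal arms, no true effect, a fraction m of the virtual arm moved, and moved patients scoring g SD worse than those who stay. With the mean of each randomised arm set to 0:

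- mean of those who stay virtual = mg
- mean of those moved = −(1−m)g
- in-person mean after transfer = −m(1−m)g/(1+m)
- spurious difference = mg + m(1−m)g/(1+m) = 2mg/(1+m)

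m = 0.10, g = 0.5: 0.10/1.10 = 0.091 SD. m = 0.20, g = 0.8: 0.32/1.20 = 0.267 SD. Both favour virtual visits. For scale, the standard error of the difference at 26 per arm is √(2/26) = 0.28 SD.

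**4. Counted as randomised.** Assume moved patients get the in-person effect, so the contrast is 0.8(1−m). Two-sided t-test:

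| m | effect | power, 26 per arm | power, 52 per arm | n per arm for 80% |
|---|---|---|---|---|
| 0 | 0.80 | 0.807 | 0.981 | 26 |
| 0.05 | 0.76 | 0.766 | 0.970 | 29 |
| 0.10 | 0.72 | 0.721 | 0.953 | 32 |
| 0.20 | 0.64 | 0.619 | 0.898 | 40 |
| 0.30 | 0.56 | 0.508 | 0.807 | 52 |

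The 52 per arm column takes the recruitment target of 104 in 9c with no losses. Section 9c intends that surplus for patients who are removed or drop out, so the column is an upper bound.

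The documents supply neither m nor g. Steps 3 and 4 are alternatives and do not add up.

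**The case against.** A reader might infer that the plan randomises patients before surgery. No passage says so. The only randomisation text comes straight after the sentence on signing at the 2-week visit, and 9g can be read as one sequence: consent at 2 weeks, randomise, notify. The rule in 9b does not prove otherwise, since randomisation on arrival at that visit triggers it equally. What stands is that the plan permits allocation before the assessment.

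A reader might also infer that early allocation is harmful in itself. The documents do not support this. Both arms have the same 2-week contact, assigned follow-up starts afterwards, and participants do not learn their arm sooner. The harm comes through the move.

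That the move is one-way is partly inherent, since a patient already seen in person has nowhere to be moved. This explains the rule but does not remove its effect on the comparison.

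A further inference would be that the trial is underpowered because of this. That does not follow: no move rate is given, and with all 104 recruits analysed power stays at or above 80% even with 30% moved. Larger numbers do not, however, reduce the bias from analysis by pathway.

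Finally, randomising all comers and analysing as randomised is a legitimate design that estimates the effect of offering virtual follow-up. Section 9i does not commit to that analysis. Fixing the randomisation time would also leave the later moves allowed by 9g, 12 and 15.

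**Conclusion.** The concern holds as an unresolved order of events with an unstated analysis rule. Consent timing is contradictory, randomisation is anchored only to consent, allocation can precede the 2-week assessment, and the resulting move affects one arm and is probably related to prognosis. The plan should be changed, because the remedy is cheap and removes the 2-week part of the crossover.

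The size is illustrative. With 10-20% moved and a gap of 0.5-0.8 SD, the bias by pathway is about a third of a standard error to one standard error at 26 per arm. Its direction depends on moved patients scoring worse, which is plausible but not documented. The loss of power as randomised assumes that moved patients get exactly the in-person effect, and it matters mainly if the number analysed is close to 52 rather than 104. How much crossover the change would prevent cannot be calculated, because the split between moves at 2 weeks and later moves is unknown.

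**What to change.** 1. Make 9a, 9b, 9g and 15 agree on consent. It may be taken at any of the contacts already listed; the eligibility condition in 9g and the omission of the day of surgery in 15 should be brought into line.
2. State one randomisation time: after the clinician's 2-week assessment, already described in 9b, has been completed and recorded. Patients whom the clinician has by then assigned to in-person follow-up are logged as consented but not randomised, with counts reported. Reword 9b to match, since no one would yet be in the virtual pathway.
3. State in 9i that every randomised patient is analysed in the assigned group, including those later seen in person under 9g, 12 or 15, and report the number of such patients.

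The clinical criteria for an in-person visit stay with the investigators, and patients keep their freedom to be seen in person.

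The cost is protocol wording, with no added visits. A few consented patients will not be randomised, and the result will apply to patients not already assigned to in-person follow-up at 2 weeks. Later crossover and its dilution remain. If the sponsor prefers to randomise all comers before the assessment, step 3 becomes essential, and the sample size should allow for a stated move rate.
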